### 6.1.1 Inclusion Criteria

The decision to prescribe either Humira or MTX must be made prior to the decision to enroll a patient in the registry. A patient will be eligible for participation if he/she meets the following criteria:

1. For a patient enrolling into the Humira arm; a pediatric patient diagnosed at any time with moderately to severely active polyarticular or polyarticular-course JIA (defined as arthritis affecting ≥ 5 joints at the time of diagnosis of polyarticular or polyarticular-course JIA) who has been prescribed Humira therapy according to the locally approved Humira product labeling and meets one of the following criteria:
  - a. Enrolled patients are 4 to 17 years of age as per approved Humira product label with the addition of polyarticular JIA patients 2 to < 4 years of age in countries with available local approval for this group of patients at the time of consent to the registry.
  - b. Newly initiated (within 24 months of registry entry) on Humira therapy and has received continuous (no more than 70 consecutive days off drug) Humira therapy, and the physician can provide available source documentation of SAEs, AEs of Special Interest, and dosing information since initiation of therapy;
  - c. Or is entering after participation (within 24 months of registry entry or, if longer, continuously treated at the same site) in an AbbVie Humira sponsored study, regardless of age or the number of joints with symptoms of polyarticular JIA, and has received continuous (no more than 70 consecutive days off drug) Humira therapy and the physician can provide available source documentation of SAEs, AEs of Special Interest, and dosing information since initiation of therapy.
2. For a patient enrolling into the MTX arm; a pediatric patient diagnosed at any time with moderately to severely active polyarticular or polyarticular-course JIA (defined as arthritis affecting ≥ 5 joints at the time of diagnosis of polyarticular or

polyarticular-course JIA) who is prescribed MTX therapy alone or in combination with other DMARDs according to the local product labeling (initiated treatment within 24 months of registry entry) and has received continuous therapy and the physician can provide available source documentation of SAEs, AEs of Special Interest, and dosing information since initiation of therapy.

3. Patients who were treated in the MTX arm of this registry and prematurely discontinued from the MTX arm due to being a non-responder, or became intolerant of MTX treatment or are in need of combination treatment with Humira therapy may be eligible to enroll into the Humira treatment arm if all ongoing AEs/SAEs have been resolved, and they meet inclusion criteria and can enroll during the registry enrollment period. In case of ongoing AEs/SAEs at the time of the treatment arm switch, the AbbVie Study Designated Physician should be contacted to assess the eligibility of patient to roll into Humira treatment arm.
4. Parent or guardian has voluntarily signed and dated an informed consent/patient authorization form, approved by an Institutional Review Board (IRB)/Independent Ethics Committee (IEC) if applicable according to local law, after the nature of the registry has been explained and the patient's parent or legal guardian has had the opportunity to ask questions. Pediatric patients will be included in all discussions as per applicable local regulations in order to obtain verbal or written assent.

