### **10.3.3 Analysis of All Treatment-Emergent SAEs and AEs of Special Interest**

All Treatment-emergent SAEs and AEs of Special Interest includes events occurring after the first recorded (initial) dose of MTX or Humira (after the first recorded dose of study drug in previous study for subjects who rollover from Study DE038 or Study M10-444 into this registry), up to 70 days after the last dose of registry drug (excluding SAEs and AEs of Special Interest occurring during TI period and AEs which occurred during the double-blind period in Study DE038 if the patient was in the Placebo arm during this period). The SAEs and AEs of Special Interest collected through the HCP process will not be included in this summary.

The number and percentage of patients experiencing treatment-emergent SAEs and AEs of Special Interest will be tabulated by body system and MedDRA® preferred term. In addition, a summary of SAEs and AEs of Special Interest by severity and relationship to registry drug will be presented. Rates (event per 100 patient-years of total exposure to Humira or MTX) of SAEs and AEs of Special Interest and the 95% confidence interval will be provided.

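### Humira-arm inclusion criterion 1 joins age, recent start and roll-over by 'one of', so read literally age alone replaces the 24-month, continuity and documentation conditions

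*Supplement*

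**What the plan says.** Section 6.1.1 of the protocol sets the Humira-arm entry rule in criterion 1. The stem asks for a pediatric patient with moderately to severely active polyarticular or polyarticular-course JIA "who has been prescribed Humira therapy according to the locally approved Humira product labeling and meets one of the following criteria". Three lettered items follow.

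- **Item a** is an age range: "Enrolled patients are 4 to 17 years of age as per approved Humira product label", extended to ages 2 to under 4 where that group is locally approved. It says nothing about start date, gaps in therapy or records.
- **Item b** is the route for recent starters: "Newly initiated (within 24 months of registry entry) on Humira therapy and has received continuous (no more than 70 consecutive days off drug) Humira therapy". The physician must also be able to supply available source documents on SAEs, AESI and dosing since the start of therapy.
- **Item c** is the roll-over route: "Or is entering after participation (within 24 months of registry entry or, if longer, continuously treated at the same site", in a sponsor Humira study, "regardless of age or the number of joints with symptoms of polyarticular JIA". It repeats the continuity and source-document conditions.

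Criterion 2, for the MTX arm, offers no alternatives. A start within 24 months, continuous therapy and available source documents are all required.

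On the analysis side, Section 10.3.3 takes "events occurring after the first recorded (initial) dose of MTX or Humira" into the All Treatment-Emergent summary. Section 10.2 runs total Humira exposure from the first recorded dose to the last registry dose plus 14 days, less treatment interruptions.

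**The concern.** Items a, b and c are not three of a kind. Item a describes who the patient is, while b and c describe how the patient came to be on Humira. Placing all three under a single 'one of' lets the first stand in for the others. A site following the text could enroll a 12-year-old who has been on commercial Humira for four years, with long gaps and without the source documents that b demands.

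Two things are at stake for the primary, safety objective. First, children who have stayed on Humira for years are a selected group, whereas MTX entrants must be within 24 months of starting. Second, the All Treatment-Emergent rate reaches back before registry entry. If a patient's early dosing dates are on record but the early events are not, person-years enter the denominator without their events, and the rate falls.

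**Working it through.** **1. The logic.** Each item is either met or not met, which gives 8 combinations. Two rules are compared: the printed one, and the one suggested by the *Or* that opens item c together with its age waiver.

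| Met | Printed rule: a or b or c | Rule: (a and b) or c |
|---|---|---|
| none | no | no |
| a only | **yes** | **no** |
| b only | **yes** | **no** |
| c only | yes | yes |
| a, b | yes | yes |
| a, c | yes | yes |
| b, c | yes | yes |
| a, b, c | yes | yes |

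The printed rule admits 7 of 8 combinations and the alternative admits 5. They differ only in the a-only and b-only rows. Reading 'one of' as exactly one does not help: a-only still qualifies, and an age-eligible child who meets b would be shut out.

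**2. Which rule was meant.** Item c waives the age condition. That waiver is needless if age is only one of three alternatives. Item c also opens with *Or*, which makes b and c the pair of alternatives. Criterion 2 treats the matching conditions as compulsory. All three fit (a and b) or c. No section states that rule.

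**3. Whether another section restores the missing *and*.** Section 6.1 speaks only of offering enrollment to eligible patients. Criterion 3 sends MTX switchers back to the same criteria. The exclusions in Section 6.1.2 concern labeling, other biologics and investigational agents. Section 6.6.2 requests retrospective events and exposure only if available. None restores it.

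**4. Possible size of the dilution.** The plan gives no figure to reproduce, so this is an illustration.

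- From the plan: about 500 Humira patients (Section 6.3) and about 1500 patient-years of registry exposure in that arm (Section 10.6).
- Assumed: 10% enter on a alone, each with 4 recorded prior years and no recorded events in those years.
- Assumed: the other 450 patients bring an average of 0 to 2 prior years each, with events fully recorded. The upper value matches item b's 24-month limit.

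Added event-free time = 50 × 4 = 200 patient-years.

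If T is the properly recorded exposure and the true rate is constant, observed rate ÷ true rate = T / (T + 200).

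- No prior time in the others: T = 1500, and 1500 / 1700 = 0.88, a dilution of about 12%.
- Two prior years each in the others: T = 1500 + 450 × 2 = 2400, and 2400 / 2600 = 0.92, a dilution of about 8%.
- No pre-registry dosing recorded for the a-only patients: nothing is added to the denominator, and the dilution is 0%.

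**The case against.** The strongest reply is that this is a drafting slip whose intent is plain, and that nothing shows any site used the loose reading. The intent is indeed clear enough to infer. But the text is the operative eligibility rule, and followed as written it gives a different result from the intended one.

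Several stronger readings are tempting, and the documents do not support them.

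- *A patient meeting b could fall outside the age range.* The stem still requires a pediatric patient treated per the local label, and exclusion 1 bars anyone who cannot be so treated. The b-only row is largely closed.
- *Every Humira patient who is not a roll-over is affected.* Anyone who meets both a and b is eligible and analyzed identically under either rule. Only a-only entrants matter.
- *A child with no dosing or event history dilutes the rate.* Total exposure starts at the first recorded dose, so unrecorded prior time never enters the denominator. Dilution needs dosing on record and events missing.
- *Early events of such patients would simply be lost.* Retrospective collection at enrollment (Sections 6.6, 6.6.2 and 9.0) applies to all entrants, not just those meeting b or c. Item b itself asks only for available documents, so it never guaranteed a complete history.
- *All Humira safety rates would look better through this dilution.* It touches one of the four safety summaries. The observational and registry treatment-emergent rates start at registry entry.

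It is also fair to say that MTX is called a reference group, that the safety analysis sections specify no test between the arms, and that users of up to 24 months, or longer for roll-overs, are admitted by design. What survives is that the plan limits prior use under b and c, and an a-only entrant escapes that limit.

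**Conclusion.** Criterion 1 is wrong as written. Within the stem, consent and exclusions, it admits an age-eligible child who meets neither b nor c, and no other section closes that route.

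The consequence is confined to a-only entrants, whose number the documents do not give. For them there are two effects. The All Treatment-Emergent rate is diluted where prior dosing is recorded and prior events are not. Separately, registry-period rates escape that dilution but still carry the selection of long-term users, whose size cannot be estimated from the documents.

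The size of the dilution is unknown. It is 0% if no pre-registry dosing is recorded for these patients, and about 8% to 12% under the stated assumption of 50 patients with 4 event-free years each. A reader might take 12% as an expected bias. It is not: it is the top of one assumed scenario, and it shrinks with every early event that retrospective collection recovers. The sample size and power in Section 10.6 do not depend on this point.

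**What to change.** Reconcile the stem of criterion 1 with its items so that it reads: meets a and b; or meets c.

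For patients already enrolled, use recorded dosing dates and documentation status to flag Humira patients who met neither b nor c. Report how many there are, and present the All Treatment-Emergent summary with their pre-registry time and events excluded. A patient without recorded prior dosing can still be counted through documentation status and has no pre-registry time to remove. If enrollment has closed, the rewording changes nobody's entry, but the count still shows whether the loose wording was used. The exclusion removes the dilution; it does not undo the selection of long-term users in the registry-period rates, so the count should be reported alongside those as well.

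The cost is one line of protocol text and one derived flag. The downside is that a few prevalent users lose their pre-registry contribution.

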### **6.1.2 Exclusion Criteria**

1. Patients should not be enrolled into the Humira or MTX arm if they cannot be prescribed and treated in accordance with the approved local Humira and/or with the local MTX product label.
2. Patients should not be enrolled into the Humira or MTX arm if they require ongoing treatment with Kineret® (anakinra), Orencia® (abatacept), Rituxan® (rituximab), Enbrel® (etanercept), Remicade® (infliximab) or any other approved biologic agents or investigational agents.

3. Patients should not be enrolled into the MTX arm if they have had prior treatment with any investigational agent or anti-rheumatic biologic therapy such as, but not limited to, Oencia® (abatacept), Enbrel® (etanercept), Remicade® (inflixumab), Rituxan® (rituximab), or Actemra® (tocilizumab).

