## 5.0 Registry Objectives

The primary objective of this registry is to evaluate the long-term safety of Humira in patients with moderately to severely active polyarticular or polyarticular-course JIA who are prescribed and treated in accordance with the approved local Humira product label under the conditions of a routine clinical setting. Patients being prescribed and treated with MTX per the approved local product label will be considered a reference group.

The secondary objective of this registry is to evaluate the long-term effectiveness of Humira in patients with moderately to severely active polyarticular or polyarticular-course JIA who are prescribed and treated in accordance with the approved local Humira product label under the conditions of routine clinical setting. In addition, the impact of treatment interruptions on the safety and effectiveness of Humira will be evaluated as well. Patients being prescribed and treated with MTX per the local product label will be considered a reference group.

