#### **6.6.4 Prior and Concomitant Medications**

Any DMARD and biologic treatments previously administered and the reason for discontinuation (i.e., AE, lack of effectiveness, intolerance or other) will be recorded. Information on the highest maintained dose, date of last administration, length of time on the medication and reason for stopping the medication will be collected in the source documents and appropriate eCRF pages.

Any medication or vaccine (including over-the-counter or prescription medicines, vitamins and/or herbal supplements) that the patient is receiving at the time of screening, and/or receives during the registry, must be recorded along with the reason for use, date(s) of administration including start and end dates, and dosage information including dose, route and frequency on the appropriate eCRF.

Intra-articular and/or soft-tissue corticosteroid injections must be captured, however the joint that is injected should be considered non-evaluable for 3 months thereafter.

Kineret® (anakinra), Orencia® (abatacept), Rituxan® (rituximab), Enbrel® (etanercept), Remicade® (infliximab) or other approved biologic agents are not to be given concurrently while participating in the registry as per the labeling for MTX and Humira.

Patients should not be enrolled into the MTX arm if they have had prior treatment with any investigational agents or anti-rheumatic biologic therapies such as, but not limited to, Orencia® (abatacept), Enbrel® (etanercept), Remicade® (infliximab), Rituxan® (rituximab), or Actemra® (tocilizumab). Patients in the MTX arm may be prescribed and treated with MTX alone, or in combination with other DMARDs but not with anti-TNFs or other biologic therapies at the time of enrollment.

Patients in MTX arm that require treatment with the biologic/anti-TNF will be excluded from the MTX treatment arm but may continue within the registry. After the Humira treatment arm enrollment is complete, if a patient in MTX treatment arm begins Humira therapy, Humira will be considered a concomitant medication.

Except for live vaccines, patients may still receive vaccines while on Humira. It is recommended that children with JIA be brought up to date with all immunizations prior to starting Humira.

The AbbVie Study Designated Physician identified in Section 7.1.8 should be contacted if there are any questions regarding concomitant or prior therapies.

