**Figure 3. Treatment Period and Treatment Interruption (TI) Period**

## 10.2 Demographics and Registry Enrollment Characteristics

Baseline characteristics: age, sex, race/ethnicity, weight, height, duration of JIA, JIA disease activity and onset type of JIA Disease onset, Rheumatoid factor (RF+, RF-), HLA-B27, body mass index (BMI), prior therapies for JIA, concomitant polyarticular JIA medications, and Humira dosage and exposure duration.

Demographics and baseline characteristics will be summarized for the All Treated Patient Population. Descriptive statistics for demographics, effectiveness, and safety parameters will be presented. Number of patients with non missing values, mean, and standard deviation will be provided for continuous variables. Counts and percentages will be provided for categorical variables. The number and percentage of patients who discontinue from the registry will be summarized, overall and by reason for discontinuation. Duration of observation in the registry, registry exposure duration and total exposure duration will be summarized as follows:

Duration of observation period = the last date of registry participation (inclusive of HCP process) – enrollment date to MTX or Humira in the registry + 1

Registry exposure duration:

(MTX arm) = last MTX dose date in the registry or the first Humira dose date in the registry whichever is earlier – first MTX dose date in the registry + 1 (The first MTX dose in the registry will be on or after the enrollment date).

(Humira arm) = last Humira dose date in the registry – first Humira dose date in the registry + 14 days – total days of any treatment interruptions (The first Humira dose in the registry will be on or after the enrollment date).

Total exposure duration:

(MTX arm) = last MTX dose in the registry or the first Humira dose date in the registry whichever is earlier – first recorded MTX dose (initial dose) + 1.

(Humira arm) = last Humira dose date in the registry – first recorded Humira dose (initial dose) + 14 – total days of any treatment interruptions. For patients who rolled over from Study DE038 and were in the Placebo arm during the double-blind period of this study, the duration of the double-blind period will be subtracted from total exposure.

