### **10.3.1 Analysis of Observational SAEs and AEs of Special Interest**

The number and percent of patients experiencing SAEs and AEs of Special Interest during the registry, regardless of whether the AEs are reported during or after the Humira or MTX treatment, will be tabulated by body system and Medical Dictionary for Drug Regulatory Activities (MedDRA®) preferred term. Rates (event per 100 patient year of observation) of SAEs and AEs of Special Interest and the 95% confidence interval will be provided. The AEs summaries will also include SAEs and AEs of Special Interest collected through the HCP process. The last contact date is defined as the last date of registry or direct to HCP process participation, whichever occurs later.

The summaries will be provided using data from the first day in registry through the last contact irrespective of drug treatment duration.

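### Prior biologic treatment is barred from the MTX arm but allowed in the Humira arm, and the planned safety rates pool biologic-naive and biologic-experienced Humira patients beside a reference group that is naive at entry

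*Supplement*

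**What the plan says.** **Eligibility.** Section 6.1.2, exclusion 3, reads "Patients should not be enrolled into the MTX arm if they have had prior treatment with any investigational agent or anti-rheumatic biologic therapy", and Section 6.6.4 repeats it. No counterpart exists for the Humira arm. Exclusion 2 covers both arms but concerns current need only: "Patients should not be enrolled into the Humira or MTX arm if they require ongoing treatment with Kineret® (anakinra", followed by other named biologics and a general clause for further biologic or investigational agents. The Humira inclusion criteria (6.1.1) set conditions on the start and continuity of Humira itself, for example "Newly initiated (within 24 months of registry entry) on Humira therapy and has received continuous (no more than 70 consecutive days off drug) Humira therapy". None requires that the child be biologic-naive.

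**Role of the MTX arm.** Under the primary safety objective (5.0), "Patients being prescribed and treated with MTX per the approved local product label will be considered a reference group". The secondary objective gives it the same role.

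**Data and analysis.** Section 6.6.4 records "Any DMARD and biologic treatments previously administered and the reason for discontinuation", together with the date of last administration and the length of time on the drug. Section 10.2 lists "prior therapies for JIA, concomitant polyarticular JIA medications, and Humira dosage and exposure duration" among the baseline characteristics. Section 10.1 uses the All Treated Population for safety. Section 10.3.1 states "Rates (event per 100 patient year of observation) of SAEs and AEs of Special Interest and the 95% confidence interval will be provided", and 10.3.2 and 10.3.3 do the same per 100 patient-years of exposure. None of these sections states a split, restriction or adjustment by prior biologic use.

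**The concern.** In any registry where the physician chooses treatment first, the arms will differ. This difference is of another kind, because an eligibility rule sets one patient characteristic to zero in one arm at entry and leaves it free in the other. With no biologic-experienced patients entering the MTX arm, adjustment cannot supply a reference rate for experienced Humira patients. Only the naive part of the Humira arm has counterparts in the reference group on this factor, and the plan as written never shows that part separately.

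At stake is how the primary safety tables will be read. If experienced patients have a different underlying rate of serious adverse events (SAEs) or adverse events of special interest (AESI), some of the gap between the Humira and MTX columns reflects who was eligible rather than which drug was taken. A reader of the tables could not tell how much.

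**Working it through.** **1. Does any passage remove the asymmetry?**

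| Point | MTX arm | Humira arm |
|---|---|---|
| Prior biologic or investigational agent | Excluded (6.1.2 no. 3; 6.6.4) | Not excluded |
| Ongoing need for another biologic | Excluded (6.1.2 no. 2) | Excluded (6.1.2 no. 2) |
| Biologic-naive condition at inclusion | Follows from exclusion 3 | None (6.1.1) |
| Split of safety rates by prior biologic | Not needed at entry | None stated (10.3.1 to 10.3.3) |

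None does. Section 10.3.4 does plan a subgroup safety table, by treatment interruption, so the protocol names such tables where it wants them.

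**2. Does the sample-size statement depend on this?** Section 10.6 compares the Humira arm with a fixed rate from Study DE038, not with MTX. Expected events in 1500 patient-years are 0.028×1500 = 42 and 0.048×1500 = 72. A one-sample Poisson score test gives (72 − 42 − 1.96×√42)/√72 = (30 − 12.70)/8.49 = 2.04, which is power of 97.9% (97.8% by the exact Poisson test), against the stated approximate 97%. The figure reproduces, and MTX eligibility does not enter it.

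**3. How far could pooling move the Humira rate?** Let p be the share of Humira patient-time from biologic-experienced patients and RR their event rate relative to naive Humira patients. Then

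pooled rate / naive rate = (1−p)×1 + p×RR = 1 − p + p×RR.

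The documents give neither input, so every value below is an assumption:

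| p | RR 0.8 | RR 1.0 | RR 1.25 | RR 1.5 | RR 2.0 |
|---|---|---|---|---|---|
| 0.1 | 0.98 | 1.00 | 1.025 | 1.05 | 1.10 |
| 0.3 | 0.94 | 1.00 | 1.075 | 1.15 | 1.30 |
| 0.5 | 0.90 | 1.00 | 1.125 | 1.25 | 1.50 |

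This is the ratio of the pooled to the naive Humira rate. It would equal the Humira/MTX ratio only if Humira had no effect of its own and nothing else differed between the arms.

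**4. What does the split cost in precision?** For Poisson counts, the standard error of a log rate is 1/√(events). If event rates are equal across strata (RR = 1), the log-scale interval widens by 1/√(1−p) in the naive stratum and 1/√p in the experienced one:
- p = 0.1: 1.05 and 3.16
- p = 0.3: 1.20 and 1.83
- p = 0.5: 1.41 and 1.41

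**5. Which summaries give the cleanest naive comparison?** The MTX arm is naive only at entry. Under 6.6.4, an MTX patient who needs a biologic leaves the treatment arm but may stay in the registry, and Humira started after Humira-arm enrolment is complete is treated as a concomitant medication. Section 10.3.1 counts to last contact whatever the treatment, so biologic time can enter the MTX observational rates. Sections 10.3.2 and 10.3.3 stop 70 days after the last dose, and 10.2 ends MTX exposure at the first Humira dose. Those two are cleaner, though not perfectly clean.

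**The case against.** The strongest reply is that this is a non-randomized registry with a descriptive reference group. Channeling is expected, prior therapies are recorded and tabulated at baseline, and subgroup tables are commonly left to a SAP. Section 10.4.1.4 mentions a SAP that is not among the documents, so such a table may exist there. That lowers confidence about the omission. It does not dispose of the point, because Section 10 already specifies the pooled tables and the improvement is concrete.

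It is also fair to say that a naive Humira stratum would still differ from MTX patients. In the EU the Humira indication requires inadequate response to at least one DMARD (4.0), and patients who switch from the MTX arm are non-responders, intolerant or in need of combination treatment (6.1). That stands, and the tables should say so.

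Several stronger readings are tempting but unsupported:
- **That the documents show prior biologics raise risk in JIA.** The hepatosplenic T-cell lymphoma text in 3.0 concerns patients who mostly had prior infliximab together with concomitant azathioprine or 6-mercaptopurine for Crohn's disease. Section 3.1 speaks of immunosuppressants used concomitantly. Neither isolates prior biologic exposure.
- **That 4.8/2.8 = 1.71 is a yardstick for a Humira/MTX ratio.** It is a contrast with Study DE038.
- **That the early Humira months after a switch count against Humira throughout.** Patients may enter up to 24 months after starting Humira, or later in the case of some roll-overs. For those already on Humira at entry, the earlier months fall outside 10.3.1 and 10.3.2; only 10.3.3 reaches back to the initial dose.
- **That the 70-day window in 10.3 applies to an earlier biologic.** It is defined for MTX and Humira, so applying it elsewhere is an extrapolation.

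**Conclusion.** The point holds as a limit on the descriptive safety comparison. By rule, the MTX reference group is biologic-naive at enrolment, and the Humira rates planned beside it pool naive and experienced patients without separating them.

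The documents fix neither the size nor the direction of the effect. Under the assumed inputs the pooled rate lies between 0.90 and 1.50 times the naive rate, with no distortion at RR = 1. A reader might infer that the pooled rates must overstate Humira's risk, or that the split would make the arms comparable. Neither follows: RR could be below 1, and prior biologic use is only one of several differences between the arms. The power statement is unaffected.

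**What to change.** Leave enrolment and the pooled Humira rates as they are. In Sections 10.3.1 to 10.3.3, or in the SAP:

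- Add Humira-arm SAE and AESI rates with 95% confidence intervals by prior biologic use (yes/no), and show the biologic-naive stratum beside the MTX reference.
- Define prior use explicitly, for example as any anti-rheumatic biologic other than Humira before the first recorded Humira dose, so that roll-over patients are not counted as experienced because of trial Humira.
- State that the split removes only the imbalance in prior biologic use at entry, not other channeling. State also that it is cleanest in 10.3.2 and 10.3.3, because MTX patients who later start a biologic may remain in the observational rates.
- Optionally, flag events close to the last dose of a previous biologic. A 70-day limit here would be the analyst's choice, not a rule taken from the protocol.

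The cost is some analysis wording and additional columns in the safety tables. No new data are needed for the biologic split, since 6.6.4 collects prior biologics with the date of last administration. The price is wider intervals in each stratum, about 1.2 times in the naive group if p = 0.3 and rates are equal, and sparser counts for malignancy and congestive heart failure, which Section 10.6 already describes as infrequent.
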